## APPENDIX D. EPI SYMPTOM QUESTIONNAIRE

### Exocrine Pancreatic Insufficiency (EPI) Symptom Questionnaire

**Instructions:** These questions ask about symptoms you may have had during the **past 7 days**. Please answer all questions by selecting the one option that best describes your experience.

1. Rate your **abdominal pain** during the past 7 days.

- None
- Mild
- Moderate
- Severe
- Very Severe

2. Rate your **bloating (feeling like you need to loosen your clothes)** during the past 7 days.

- None
- Mild
- Moderate
- Severe
- Very Severe

3. Rate your **nausea** during the past 7 days.

- None
- Mild
- Moderate
- Severe
- Very Severe

4. Rate your **vomiting** during the past 7 days.

- None**
- Mild**
- Moderate**
- Severe**
- Very Severe**

5. Rate your **gas (flatulence)** during the past 7 days

- None**
- Mild**
- Moderate**
- Severe**
- Very Severe**

6. Rate your **constipation** during the past 7 days.

- None**
- Mild**
- Moderate**
- Severe**
- Very Severe**

7. Rate your **foul smelling stools** during the past 7 days.

- None
- Mild
- Moderate
- Severe
- Very Severe

8. Rate your **greasy or fatty stools** during the past 7 days.

- None
- Mild
- Moderate
- Severe
- Very Severe

9. Rate your **abdominal cramps** during the past 7 days.

- None
- Mild
- Moderate
- Severe
- Very Severe

10. Rate your **diarrhea** during the past 7 days.

- None
- Mild
- Moderate
- Severe
- Very Severe

11. Rate your **lack of appetite** during the past 7 days.

- None
- Mild
- Moderate
- Severe
- Very Severe

12. Rate your **tiredness** during the past 7 days.

- None
- Mild
- Moderate
- Severe
- Very Severe

APPENDIX E. BRISTOL STOOL CHART

## Bristol Stool Chart

Type 1		Separate hard lumps, like nuts (hard to pass)
Type 2		Sausage-shaped but lumpy
Type 3		Like a sausage but with cracks on its surface
Type 4		Like a sausage or snake, smooth and soft
Type 5		Soft blobs with clear-cut edges (passed easily)
Type 6		Fluffy pieces with ragged edges, a mushy stool
Type 7		Watery, no solid pieces. Entirely Liquid

1.0 Introduction

This Statistical Analysis Plan (SAP) describes the statistical analyses for CREON or ABT-SLV245 Study M16-142 titled "Creon® (pancrelipase) therapy for subjects with exocrine pancreatic insufficiency (EPI) due to pancreatic cancer: A double-blind, randomized, parallel design with 2 dose cohorts of pancrelipase in resected pancreatic cancer subjects and an open-label single dose cohort in non-resected pancreatic cancer subjects".

Study M16-142 examines the effects of Creon in subjects with resected pancreatic cancer receiving 2 dosing cohorts, and one dosing cohort in non-resected pancreatic cancer subjects.

The SAP will not be updated in case of administrative changes or amendments to the protocol unless the changes impact the analysis.

Unless noted otherwise, all analyses will be performed using SAS Version 9.4 (SAS Institute Inc., Cary, NC 27513) or later under the UNIX operating system.

This SAP includes changes to analyses described in the protocol version 3.0 dated 22 November 2019. Details are outlined in Section 12.0.

2.0 Study Design and Objectives

2.1 Objectives, Hypotheses, and Estimands

The objective of this study is to evaluate the effects of Creon[®] (pancrelipase) on stool fat and EPI symptoms in subjects with resected pancreatic cancer receiving 2 dosing cohorts, and one dosing cohort in non-resected pancreatic cancer subjects.

The hypothesis for the primary objective of a significant change in stool fat from Baseline to Week 1 will be tested at 2-sided 5% α -level for each dose cohort in the resected pancreatic cancer population and for the non-resected population as well.

For each subject, the average stool fat per day (grams/day) from the stools collected in last 48 hours prior to the baseline visit and prior to the Week 1 visit will be calculated and the difference between those 2 visits will be calculated.

The estimand corresponding to the primary objective is:

Mean change in stool fat from baseline to Week 1 will be calculated in subjects treated with either high dose of CREON (72,000 USP units (Lipase) with meals/36,000 USP units (Lipase) with snacks) or low dose of CREON (12,000 USP units (Lipase) with meals/6,000 USP units (Lipase) with snacks) in the Evaluable Analysis Set for stool fat in the Resected Pancreatic Cancer regimen. Subjects who do not have an evaluable stool sample (described in Section 9.2.3) at both Baseline and Week 1 will be excluded from the analysis.

2.2 Study Design Overview

This is a Phase 4, randomized, double-blind, parallel design study with 2 dose cohorts in resected subjects, and an open-label single dose cohort in non-resected subjects with EPI due to pancreatic cancer.

Resected subjects are defined as subjects who had surgery to remove the pancreatic cancer.

Non-resected subjects are defined as unresectable, resectable, and borderline resectable or pancreatic cancer subjects who did not have a pancreatectomy due to cancer and do not plan to undergo such a surgery during study participation.

At Day 1, eligible resected subjects will be randomized in 1:1 ratio to one of following dose cohorts, and will remain on blinded therapy for 13 weeks:

 Low dose (cohort of 12,000 USP units (Lipase) with meals/6,000 USP units (Lipase) with snacks)

2. High dose (cohort of 72,000 USP units (Lipase) with meals/36,000 USP units (Lipase) with snacks)

At Weeks 1, 5, or 9, subjects who meet dose modification criteria described in Section 2.4 will be titrated once by the IRT to the following dose cohorts in a blinded fashion:

- Subjects receiving the lower dose will escalate to pancrelipase 72,000 USP units (Lipase) with meals/36,000 USP units (Lipase) with snacks.
- Subjects receiving the high dose will continue receiving the high dose throughout the study. In order to maintain the blind of the study, subjects in the high dose cohort will also receive a matching placebo and will not exceed the maximum dose per the USPI.

Non-resected subjects in the open-label dose cohort will receive pancrelipase at a dose of 72,000 USP units (Lipase) with meals/36,000 USP units (Lipase) with snacks during the entire duration of the study.

No interim analyses are currently planned. Study sites and resected subjects in the double-blind cohorts will remain blinded for the treatment period of the study.

In support of the primary endpoints, it is critical for subjects, who were on PERT before the start of the study, to stop PERT a week prior to Day 1 and to initiate stool collection 48 hours prior to Day 1 and Week 1 visits. The schematic of the study is shown in Figure 1.

The schematic of the study is shown in Figure 1.

Figure 1. Study Schematic

⁴: No PERT A week prior to Day 1

2.3 Treatment Assignment and Blinding

Eligible resected subjects will be randomized in 1:1 ratio to one of following dose cohorts, and will remain on blinded therapy throughout the study treatment period (13 weeks):

- Low dose (cohort of 12,000 USP units (Lipase) with meals/6,000 USP units (Lipase) with snacks) (n = 36)
- High dose (cohort of 72,000 USP units (Lipase) with meals/36,000 USP units (Lipase) with snacks) (n = 36)

Subjects in the non-resected population will receive open-label Creon (cohort of 72,000 USP units (Lipase) with meals/36,000 USP units (Lipase) with snacks) for 13 weeks (n = 20).

The randomization is central with no stratification.

2.4 Sample Size Determination

Resected Subjects: 72 subjects total will be enrolled (36 subjects per dose cohort). After adjusting for a dropout rate of 16%, the study will have 60 evaluable subjects for the evaluation of stool fat at Week 1. This sample size will have an approximately 99% power to detect a 20 g stool fat reduction in mean stool fat from Baseline in each dose cohort assuming that the standard deviation for the change is 25 g or approximately 94% power to detect a 10 g stool fat reduction in mean stool fat from baseline assuming that the SD for the change is 15 g. The type I error rate is 0.05 (2-sided).

In addition, the study will have an approximately 86% power to detect a difference of 20 g between 2 dose cohorts in mean stool fat change from Baseline, assuming the same standard deviation of 25 g for both dose cohorts. The power will drop to 63% if the difference is 15 g.

Non-Resected Subjects: Up to 20 subjects will be enrolled. This is an exploratory cohort and no formal statistical tests are planned for this cohort.

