### Primary Analysis

The primary efficacy endpoint is the change in stool fat from Baseline (Day 1) to Week 1. Within each dose cohort, a paired t-test will be performed to test the null hypothesis that the mean stool fat change is equal to zero. For comparison between dose cohorts, the change from Baseline will be analyzed using an analysis of covariance model including treatment as a fixed effect and Baseline stool fat as the covariate.

Details on the primary and other efficacy analyses are provided in the SAP.

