9.4 Secondary and Additional Efficacy Analyses

9.4.1 Stool Fat

Resected Subjects

For comparison between dose cohorts for change in stool fat from Baseline to Week 1, the ANCOVA model including treatment as fixed effect and baseline stool fat as the covariate as described for the primary analysis will be used. The least square mean estimate of the difference between two treatment groups in change from baseline in stool fat will be provided along with the 95% CI and P value. The analysis will be performed using the EAS-SF and EAS-SF-SUPP set for the resected population only.

Non-Resected Subjects

The change in stool fat from Baseline to Week 1 will be analyzed using an analysis of covariance (ANCOVA) model including Baseline stool fat as the covariate. The least square mean estimates for change in stool fat along with its two-sided 95% CI will be provided. The null hypothesis of no change in mean stool fat from Baseline to Week 1 will be tested at 2- sided 5% α – level in EAS-SF.

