9.4.3 Stool Consistency

Stool consistency will be collected once a day for 7 days prior to each visit using the Bristol Stool Chart and will be characterized based on the typology below for the analysis. The proportion of days with watery consistency during 7-day period prior to each visit will be calculated at each visit for each subject. The analyses will be performed using the population and treatment groups as described in Table 1 in Section 4.2.

- A Wilcoxon paired signed rank test will be performed for comparison of the proportion of days with watery stool consistency of Week 1 to that at Baseline within each dose cohort in the resected population. Similar test will be performed in the non-resected population as well.
- For comparison of change in the proportion of days with watery stool consistency from Baseline to Week 1 between two dose cohorts will be assessed through the non-parametric Wilcoxon Rank-Sum test in the resected population.

- Descriptive statistics will be provided for proportion of days with watery stool consistency at Week 1 (Day 8), 5, 9 and 13 as well as change from Baseline for each visit in both the resected and non-resected population.
- The number and percentages of subjects with 7 different types of stool consistency reported and 2 different types of characterization of stool consistency as described in Table 3 will be summarized per day for 7 days prior to Baseline (Day 1) and 7 days prior to Week 1 (Day 8) visit for the non-resected population and for each analysis treatment group in the resected population.

Table 3. Characterization of Bristol Stool Chart for Analysis

Stool Type (Score)	Characterization
Type 1 (1), Type 2 (2), Type 3 (3), Type 4 (4), Type 5 (5)	Hard/Normal
Type 6 (6), Type 7 (7)	Watery

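### The SAP both excludes and plans tests for the non-resected cohort, and its baseline-only ANCOVA gives an interval too narrow for the population mean change unless change and baseline are uncorrelated

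*SAP*

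**What the plan says.** SAP 2.4 gives the size of the non-resected cohort, "Up to 20 subjects will be enrolled", and then states: "This is an exploratory cohort and no formal statistical tests are planned for this cohort".

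Other SAP sections plan such tests:

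- SAP 2.1 sets the stool fat hypothesis at a two-sided 5% level "for each dose cohort in the resected pancreatic cancer population and for the non-resected population as well".
- SAP 9.4.1, under the non-resected heading, specifies an ANCOVA with baseline stool fat as the only covariate and a least-squares mean with a 95% CI. It adds: "The null hypothesis of no change in mean stool fat from Baseline to Week 1 will be tested", two-sided at 5%, in the evaluable stool fat set.
- SAP 9.4.3, after describing the paired signed rank test for watery-stool days in the resected cohorts, says: "Similar test will be performed in the non-resected population as well".
- SAP 9.4.2 (stool frequency) and 9.4.4 (EPI symptom score) use an ANCOVA for the change to Week 1 and restrict the treatment term to the resected population. For the non-resected cohort the model therefore contains baseline alone. Neither section writes out a null for this cohort, but SAP 9.1 puts all tests at a two-sided 0.05.

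Protocol 7.3 describes the primary analysis this way: "Within each dose cohort, a paired t-test will be performed to test the null hypothesis that the mean stool fat change is equal to zero". Protocol 3.2 defines that primary endpoint for resected subjects only.

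**The concern.** There are two linked problems. First, the SAP cannot be followed as written: a stated null at a stated alpha is a test on any ordinary reading, and 2.4 says there will be none. Whoever programs the tables must choose which section to obey.

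Second, if 9.4.1 is followed, the model does not match the hypothesis. With one arm there is no imbalance to adjust for, so the baseline covariate leaves the estimate unchanged. It does remove from the standard error the part of the variation in change that baseline explains. That part is real sampling variation when the question is the mean change in the population.

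At stake is an uncontrolled, open-label cohort with no stated power or precision basis. It would be reported with a P value that one section says will not exist, and with an interval that may cover less than its label.

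**Working it through.** **The plan's own figures.** No power or precision figure is given for the non-resected cohort. The resected figures in SAP 2.4 reproduce with 72 × (1 − 0.16) = 60.5, so 30 per arm, using the noncentral t:

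- Within cohort, noncentrality (δ/σ)√n: 20/25 × √30 = 4.38 gives 98.8% (stated 99%); 10/15 × √30 = 3.65 gives 94.2% (stated 94%).
- Between cohorts, noncentrality (δ/σ)√(n/2): 20/25 × √15 = 3.10 gives 86.1% (stated 86%); 15/25 × √15 = 2.32 gives 62.8% (stated 63%).

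Those figures are sound and are not part of this point.

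**The model.** Let B be baseline and C the change. Fit C = a + b·B to n subjects.

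- The least-squares mean at the sample mean baseline is a + b·mean(B) = mean(C), the raw mean change.
- Its model SE is s_resid/√n.
- The one-sample (paired) SE is SD(C)/√n.
- The ratio of the two is about √(1 − ρ²), where ρ is the correlation of change with baseline.

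The ratio is 1 only if ρ = 0.

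**From visit correlation to ρ.** Let r be the Baseline/Week 1 correlation and k the Week 1 SD divided by the Baseline SD. Then

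ρ = (rk − 1)/√(1 + k² − 2rk).

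With equal SDs (k = 1) this becomes |ρ| = √((1 − r)/2), and the ratio is √((1 + r)/2). For r = 0.5, |ρ| = 0.50 and the ratio is √0.75 = 0.866. For r = 0, |ρ| = 0.71 and the ratio is √0.5 = 0.707.

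**Inputs.** n = 20 is the SAP 2.4 maximum. r and k are not in the documents and are assumed over a range. The simulation uses bivariate normal data with no true change and at least 100,000 cohorts per setting. Each tests the least-squares mean on n − 2 degrees of freedom and compares it with the paired t-test.

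| r (k = 1) | abs(ρ) | Type I error, ANCOVA | CI too narrow by about |
|---|---|---|---|
| 0.9 | 0.22 | 5.6% | 2% |
| 0.8 | 0.32 | 6% | 5% |
| 0.5 | 0.50 | 8.5% | 13% |
| 0.2 | 0.63 | 12% | 22% |
| 0 | 0.71 | 15% | 29% |

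The paired t-test stays close to 5% throughout. Coverage of the ANCOVA interval is 100% minus the type I error, so 91.5% at r = 0.5. With 17 evaluable subjects (20 less the 16% dropout assumed for the resected cohorts, itself an assumption here) the results are nearly the same.

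**Unequal SDs.** Baseline is collected off enzyme therapy and Week 1 on treatment, so k below 1 is plausible. With k = 0.5:

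- r = 0.5: ρ = (0.25 − 1)/√0.75 = −0.87.
- r = 0: ρ = −1/√1.25 = −0.89.

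The nominal 95% interval then covers about 64% to 69%. In the other direction ρ reaches zero when k = 1/r, that is, when the Week 1 SD exceeds the Baseline SD by exactly that factor.

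**The contradiction.** This needs no arithmetic. SAP 2.4 excludes tests, 2.1 and 9.4.1 specify one at 5%, and 9.4.3 specifies another. The signed rank test in 9.4.3 is affected only by this conflict, not by the standard-error problem.

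**The case against.** *The word formal may mean powered or confirmatory.* The sentence in 2.4 sits in a sample-size section and may only explain why no power is given. The protocol synopsis also says a subset of the resected analyses will be run on the non-resected data. This stands as a reason not to assume that 2.4 is the sentence to keep. It does not remove the conflict, because 9.4.1 writes out a null and an alpha.

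*The interval is not simply wrong.* It is valid conditional on the observed baselines, that is, for the mean change at exactly the sample mean baseline. This stands. A reader might infer that ANCOVA is invalid in any single-arm setting; that is too strong. The mismatch is with the unconditional null in 9.4.1.

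*The size is unknown.* This also stands. Both visits use 48-hour collections from the same person about a week apart, so a high correlation cannot be excluded, and at 0.8 or 0.9 the inflation is about one percentage point or less. A reader might take 8% to 15% as the finding, but the documents do not support choosing only the low correlations.

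*The protocol does not prescribe a paired t-test for this cohort.* Correct. A reader might infer from Protocol 7.3 that the SAP overrides it here, but that text concerns the resected primary endpoint. It shows only that a suitable within-cohort method was already at hand.

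*The same mechanism reaches the resected within-cohort least-squares means in SAP 9.3.2.* It does, to a smaller degree: at 30 per arm, about 6.8% at |ρ| = 0.5 and 10.3% at 0.7. The between-dose comparison is not affected by it.

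**Conclusion.** The contradiction is explicit and needs no assumption. The direction of the standard-error problem is settled by algebra: for the population mean change, the baseline-only ANCOVA interval is too narrow unless change and baseline are uncorrelated. Its size is conditional. With 20 subjects, normal data and equal visit SDs, type I error lies between about 5.6% and 15% as the Baseline/Week 1 correlation falls from 0.9 to 0. It is larger if variability falls on treatment. The documents cannot narrow that range.

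A reader might infer that a main trial conclusion is compromised by this test. The documents do not support that. Non-resected stool fat is an additional endpoint in an exploratory cohort, and SAP 12.0 lists only the resected groups for primary testing and disclaims any registrational purpose. The correction is worth making because it is cheap and the SAP is otherwise ambiguous, not because a primary or secondary result depends on it.

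**What to change.** 1. For non-resected stool fat, stool frequency and EPI symptom score (SAP 9.4.1, 9.4.2 and 9.4.4), replace the baseline-only ANCOVA with the mean change from Baseline to Week 1 and a one-sample (paired) t-based 95% CI.

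2. Reconcile SAP 2.4 with 2.1, 9.4.1, 9.4.2, 9.4.3 and 9.4.4 in one of two ways:
   - remove the non-resected tests, including the signed rank test, and report estimates with intervals only; or
   - amend 2.4 to say that nominal exploratory tests without a power basis are planned, and use the paired t-test for the three endpoints above.

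Either route is acceptable; the choice between them is a matter of preference. What matters is that all six sections agree, since editing only 2.1, 9.4.1 and 9.4.3 would leave the same model in 9.4.2 and 9.4.4.

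The cost is SAP wording and a wider reported interval: about 1/0.866 = 1.15 times as wide at a correlation of 0.5 with equal SDs. No data collection changes.

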2.5 Dose Modification

Dose modifications will be determined by a "dispensation score" calculated in EDC based on the responses to Questions 7, 8 and 10 from the EPI Symptom Questionnaire (Appendix D). The "dispensation score" will be then entered in IRT by the sites. Whether the subject needs dose modification will be determined by the "dispensation score" and IRT will then dispense the corresponding drug accordingly. The process will keep the site staff and the subjects blinded on whether the subject will be dose modified or not. The dose modification process including the details of the IRT dispensation score derivations are documented in the Study M16-142 Documentation of Key Decision dated 09 February 2020. The general dose modification rules are described as below.

Calculation of Total Score for Dose Modification:

The score for dose modification will be calculated by assigning the following values to each one of the responses to Questions 7, 8, and 10 in the EPI symptom questionnaire: none = 0, mild = 1, moderate = 2, severe = 3, very severe = 4. The total score for dose modification will be calculated as the sum of the responses to Questions 7, 8, and 10 within each visit. If none of the three questions are answered, the score will be noted as NULL.

The criteria for dose modification are described below:

- a. If current score = NULL, then maintain dose.
- b. If the previous score is NULL and the score for the current visit is available, then replace the previous score with the last available visit score as the previous score and follow the dose escalation criteria d) e) or f).
- c. If the Baseline visit score and all other visit scores prior to the present visit are NULL but the present visit score is available, then maintain dose.
- d. If current score <= 2, then maintain dose.
- e. If current score > 2 and there is less than 30% improvement from the previous score, i.e., current score > $(0.7 \times \text{previous score})$, then increase dose.

f. If current score > 2 and there is 30% or more improvement from the previous score i.e., current score <= $(0.7 \times \text{previous score})$, then maintain dose.

The subjects, site staffs and Abbvie site monitors will be blinded to the detailed dose modification criteria as well as the subject's dose medication status.

Resected Subjects

The dose for resected subjects in the low dose cohort (12,000 USP units (Lipase) with meals/6,000 USP units (Lipase) with snacks) will be modified to the high dose (72,000 USP units (Lipase) with meals/36,000 USP units (Lipase) with snacks) at Week 1, 5, or 9 if the dose modification criteria defined above are met. Subjects randomized to the high dose cohort are not dose modified.

Only one dose modification will be permitted throughout the study. For subjects who have already experienced dose escalation, they will remain on the high dose level for the rest of the treatment duration, even if they continue to meet the dose escalation criteria in the subsequent visit(s). No further dose escalation is allowed.

Non-Resected Subjects

Non-resected subjects in the open-label population will continue to receive pancrelipase at a dose of 72,000 USP units (Lipase) with meals/36,000 USP units (Lipase) with snacks during the study; there will be no dose modification.

